STUDY TITLE: Oral Penicillin Challenge in the Pediatric Emergency Department

NCT number: NCT03404804

Document date: 1aug22 last continuing review approval

PRINCIPAL INVESTIGATOR: [name], DO, MS

STUDY TITLE: Oral Penicillin Challenge in the Pediatric Emergency Department

A. PURPOSE OF THE STUDY

The purpose of this study is to utilize a parent-reported penicillin allergy questionnaire in a pediatric emergency department (PED) and demonstrate that providers will administer, and families will be willing to receive an oral penicillin challenge in those children deemed to have non-allergic and low-risk symptoms of true penicillin allergy.

B. HYPOTHESES / SPECIFIC AIMS

Aim 1: Demonstrate that a low-risk group of children with reported penicillin allergy will complete an oral penicillin challenge during a pediatric emergency department visit.

Hypothesis 1a: Providers will administer an oral penicillin challenge in the PED to children identified as having non-allergic and low-risk allergy symptoms.

Hypothesis 1b: Children with non-allergic and low-risk allergy symptoms will complete an oral penicillin challenge in the PED.

Aim 2: Conduct follow-up one day after oral challenge for all children and seven days after oral challenge for patients discharged with a prescription antibiotic to determine if a delayed or T-Cell mediated reaction occurs after exposure to multiple doses of penicillin or any other antibiotic prescribed at discharge.

Hypothesis 2a: Next day contact will be possible for over 95% of children who complete an oral challenge to demonstrate the ability to evaluate symptoms after PED discharge.

Hypothesis 2b: Seven-day follow-up will be completed in at least 90% of children who are discharged on a penicillin or other antibiotic to demonstrate the ability to monitor for delayed or T-Cell mediated reaction following the administration of multiple doses of penicillin.

Aim 3: Examine health care outcomes and prescription-related costs associated with illness treatment plans in children who are de-labeled as penicillin allergic after an oral challenge.

Hypothesis 3a: Health care outcomes (allergic reactions, number of illnesses, antibiotics prescribed, and ER/Urgent Care/Primary care visits) will be similar between children de-labeled as penicillin allergic compared to the general population.

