- 9) If there is a serious or anaphylactic reaction, emergency medicine will be given right away. The medicine is called epinephrine and comes in an Epi-Pen. Additional medications that could also be given include steroids, Benadryl, Zantac, and IV fluids. If a reaction occurs that requires emergency medicine the patient or the patient’s insurance are liable for the cost of this continued treatment. Their liability also includes any copay that may associated with the use of their insurance or if insurance does not cover the inpatient hospitalization. The potential costs for treating a reaction in which a patient is hospitalized may be thousands of dollars. However, we believe the risk of this occurrence to be very low as the incidence of true IgE mediated penicillin allergy is estimated to be in the range of 0.004% to 0.015%.^{21,22} Additionally, those children deemed low-risk on our questionnaire, likely never had an IgE mediated allergic reaction to begin with and are most likely falsely labeled as penicillin allergic. Families are also notified in the Oral Challenge consent and assent to call 9-1-1 and seek immediate medical attention if any serious reaction occurs after their child leaves the ED.
- 10) At the end of the visit the diagnosis will be recorded, and treatment/discharge will continue at the discretion of the PED physician/nurse practitioner/physician assistant . All patients who receive an oral challenge will be given an Allergy Oral Challenge Information sheet.
- 11) If a child is negative after oral challenge and has no need for an antibiotic at the time of discharge, the child will be discharged home.
- 12) If a child is negative after oral challenge and treatment would indicate a penicillin antibiotic, the child will be discharged home with a penicillin antibiotic.
- 13) Family contact information will be obtained in the questionnaire and utilized to complete follow-up phone calls after PED oral challenge.
- 14) The patient’s PMD (primary medical doctor) and pharmacy of record will be notified of the testing and results via fax within 7 days. Fax confirmations will be kept by the study team in the patient’s research file.

Aim 2: Conduct follow-up one day after oral challenge for all children and seven days after oral challenge for patients discharged with a prescription antibiotic to determine if a delayed or T-Cell mediated reaction occurs after exposure to multiple doses of penicillin or any other antibiotic prescribed at discharge.

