
Design/setting and study population:

This study will include all children from Aim 1 who underwent an oral challenge in the PED after being determined to have low-risk symptoms on the allergy questionnaire.

Study Procedure (Figure 1, Aim 2)

- 1) A follow-up phone call will be made to all families whose child received an oral challenge.
- 2) If a family receives a one-time dose of antibiotic but does not receive a prescription for a penicillin antibiotic then they will be called on day 1 by a research team member who will administer a 5-minute allergy questionnaire that will review any possible symptoms of allergic reaction following the ED visit.
- 3) If a family receives a penicillin antibiotic prescription following the oral challenge, then they will be called on days 1 and 7 by a research team member for a 5-minute allergy questionnaire that will review any possible symptoms of allergic reaction following the ED visit.
- 4) The patient's primary medical provider will also be notified of the oral challenge results for both groups of patients via fax within 7 days of the oral challenge date.

Aim 3: Examine health care outcomes and prescription-related costs associated with illness treatment plans in children who are de-labeled as penicillin allergic after an oral challenge.**Design/setting and study population:**

This study will include children identified as having low-risk symptoms of allergy from Aim 1 who underwent an oral challenge (Group 1), and those who did not undergo an oral challenge in the PED (Group 2).

Study Procedure (Figure 1, Aim 3)

- 1) A follow-up 5-minute phone survey will be completed by research staff to the family. This follow-up will occur after their initial PED visit at 6 and 12 months.
- 2) The follow-up survey will include questions on health care outcomes since the PED visit that include but are not limited to: the number and type of diagnosed infections, number and type of antibiotics given, and allergic reaction history.

E. TOTAL NUMBER OF HUMAN RESEARCH PARTICIPANTS PROPOSED FOR THIS STUDY AT THIS SITE AND GLOBALLY. WHAT ARE THESE NUMBERS BASED ON?

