We have determined that we need 100 low-risk patients to complete the oral challenge at each of the three sites participating including here at Children's Hospital of Wisconsin. We will consent for questionnaire-screening approximately 500 children to achieve that number. This number is based off of our previous study; during that study 50 patients were approached per month for survey participation, 80% (40) agreed to participation, and 25% (10) of patients were found to have high-risk symptoms of allergy and thus were found to be ineligible. If 50% of patients with low-risk symptoms will have either provider/family refusal to oral challenge this will leave approximately 15 patients per month to complete an oral challenge and complete this portion of the study in approximately 7 months.

F. DRUGS OR PROCEDURES

Patient's family or guardian will be asked to answer an allergy symptom questionnaire that will be administered via an iPad. Patient's charts who are between the ages of 2-16 whose family has indicated an interest in allergy oral challenge will be reviewed.

If a child is eligible as defined in the questionnaire for allergy oral challenge and the family completes the challenge, then a gift card in the amount of \$50 will be provided for their time.

If a family completes all the telephone follow-up questionnaires at 6 and 12 months they will be mailed a \$25 gift card at the conclusion of each of the follow-up calls. (total of \$50 in follow-up stipends for full participation over one year.)

The allergy challenge consists of an oral amoxicillin challenge in the PED. A nurse will administer the oral challenge and will also be present during the process all of which will occur in the PED.

A follow up telephone survey monitoring for any adverse side effects/allergic reactions will be completed within 24 hours of the allergy oral challenge. If a patient receives a prescription for a penicillin or any other antibiotic then a follow up call will be made to monitor for any adverse side effects/allergic reactions at 7 days as well. Patients will also receive discharge instructions relevant to the study with phone numbers to call with questions.

A follow-up 5-minute phone survey will be completed by research staff to families of groups after their initial PED visit at 6 and 12 months. PI will review these results monthly or as relevant (notified by the study team) to monitor the long-term outcomes and safety of the protocol.

G. RISK CATEGORY:

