3) Research staff is present in the PED 16 hours per day on weekdays and 10 hours per day on weekends allowing for more than sufficient coverage to meet enrollment goals. We will limit administration of the oral challenge to 3 patients per day in an attempt to limit PED flow disruption. Administration of the questionnaire alone should not be disruptive to flow.

The appropriately trained research personnel will be identified in the registration page of this submission.

O. Statistical Analysis plan

Data collection and Management:

All children will be assigned a unique study ID number. Responses to the allergy questionnaire and oral challenge will be captured on a tablet computer. Data will be entered into RedCap (<http://www.project-redcap.org/>). Additional data points include child’s age in years, child’s sex, race/ethnicity (determined by parent and consistent with NIH guidelines) and visit number.

For children who receive an oral challenge, additional data will include the time of medication administration and time of discharge from the PED. The details of any reaction that occurred and corresponding treatment will also be captured. Final ED disposition will be recorded, and home contact information confirmed for follow-up.

Data Analysis:

Descriptive statistics will be used to summarize baseline patient characteristics, allergy questionnaire, and oral challenge data. The percentage of patients who are eligible for oral challenge will be determined. The percent

of patients/families that refuse an oral challenge or that have providers who are unwilling to conduct an oral challenge in the PED will be documented. The frequency of positive oral challenges will be analyzed and reported using a 95% confidence interval. Descriptive statistics will be used to summarize day 1 and 7 patient characteristics and follow-up questionnaire data. The percentage of patients that are lost to follow-up after an oral challenge will be determined. The frequency of delayed allergic reactions after oral challenge will be analyzed and reported using a 95% confidence interval. SPSS version 22 will be used to perform all analyses. SPSS version 22 will be used to perform all analyses.

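### Aim 2 concerns repeated dosing, but the plan does not state that the day-7 call records doses taken, and the delayed-reaction rate has no repeated-dose denominator

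*Combined protocol and SAP*

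**What the plan says.** Section D states the purpose of the Aim 2 follow-up as "to determine if a delayed or T-Cell mediated reaction occurs after exposure to multiple doses of penicillin or any other antibiotic prescribed at discharge". Hypothesis 2b in Section B says the seven-day contact should show the ability "to monitor for delayed or T-Cell mediated reaction following the administration of multiple doses of penicillin".

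The day-7 call is described in two places. Section D, Aim 2, Study Procedure, step 3 says: "If a family receives a penicillin antibiotic prescription following the oral challenge, then they will be called on days 1 and 7", and gives the content as a call "for a 5-minute allergy questionnaire that will review any possible symptoms of allergic reaction following the ED visit". Section F, which covers a prescription for a penicillin or any other antibiotic, says: "then a follow up call will be made to monitor for any adverse side effects/allergic reactions at 7 days as well".

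Section O lists the extra data for challenged children. It begins: "For children who receive an oral challenge, additional data will include the time of medication administration and time of discharge from the PED". It goes on to reaction details and treatment, disposition and contact information. For the analysis it says: "Descriptive statistics will be used to summarize day 1 and 7 patient characteristics and follow-up questionnaire data", and: "The frequency of delayed allergic reactions after oral challenge will be analyzed and reported using a 95% confidence interval".

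**The concern.** The question in Aim 2 depends on exposure, but a child joins the day-7 group by being handed a prescription. Neither description of the call, nor the Section O data list, names whether the course was filled or started, the days taken, or stopping and switching. These families came to the visit reporting a penicillin allergy, so an unfilled or shortened course is foreseeable. The protocol's own background section also shows that the distinction matters: it reports a 5-day challenge study separately for 417 full and 44 partial courses.

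The denominator is a second, separate gap. Section O describes the delayed-reaction frequency only by reference to the oral challenge. Every challenged child gets a day-1 call, and most are expected to receive one dose only. Nothing in the wording keeps those children out of the figure.

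At stake is whether the delayed-reaction result can be read as evidence about repeated dosing. If exposed, unexposed and single-dose children are pooled, the rate does not answer Aim 2, and it will be too low for repeated exposure whenever the other children react less often.

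**Working it through.** **Inputs**
- Completed challenges: 50 (Section O, Sample Size Justification). Section E instead gives 100 per site at three sites.
- Share sent home with a prescription antibiotic: about 20% (Section O).
- Share of prescribed children who take repeated doses: not given. I assume 70% to 100%.

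**Reproducing the plan's figures**
- 50 × 0.20 = 10 prescribed and 50 − 10 = 40 with one dose only, as Section O states. The 10 counts prescriptions for any antibiotic, not children who took repeated doses of a penicillin.
- Section C gives a 96.4% lower limit for 100 of 100. The exact (Clopper-Pearson) formula gives 0.025^(1/100) = 0.9638, which agrees, so I use the same method below.

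**Upper 95% limit with zero delayed reactions: 1 − 0.025^(1/n)**

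| Denominator | n | Upper limit |
|---|---|---|
| All challenged children | 50 | 7.1% |
| All prescribed children, all exposed | 10 | 30.8% |
| 90% of prescribed exposed | 9 | 33.6% |
| 70% of prescribed exposed | 7 | 41.0% |

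With Section E's 100 per site, 100 × 0.20 = 20 prescribed. The limit is then 16.8% if all are exposed and 23.2% if 14 are (70%). For 300 children, 300 × 0.20 = 60 prescribed, and the limits are 6.0% for 60 and 8.4% for 42.

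**Point estimate**

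The pooled rate is a weighted average:

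rate = (exposed share × rate in exposed) + (unexposed share × rate in the others).

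If the others have no delayed reactions, the factor is the exposed share: 9/10 = 0.9 or 7/10 = 0.7 within the prescribed group, and 10/50 = 0.2 if all 50 are the denominator. One reaction then reads as 1/7 = 14.3%, 1/10 = 10.0% or 1/50 = 2.0%, depending only on who is counted. The factors are worst cases, because every child took the challenge dose and could react late to it. Any such reactions bring the factor nearer to 1.

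**Partial exposure in the cited study**

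44/(417 + 44) = 44/461 = 9.5% had a partial course. The setting differs and the reasons are not given, so this shows only that incomplete courses occur.

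**The case against.** Several stronger readings are tempting, and the documents do not support them.

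- A reader might infer that the call fails to collect exposure. The questionnaire is not reproduced, and the figure cited for the procedure is not shown. All that can be said is that the plan does not state that exposure is recorded.
- A reader might infer that unexposed children are to be counted as tolerating repeated doses. No section defines a tolerated outcome. That such a child becomes a non-event is a consequence of the missing denominator, not a stated rule.
- A reader might infer that a reaction that led to stopping and then resolved would be missed. The call reviews any symptoms since the visit, and staff administer it as a questionnaire, so a resolved reaction is in scope. What is not described is a record of the stop or switch itself.
- A reader might infer that no fill or antibiotic data exist. The cost analysis in Section O presumes fill data, and the 6- and 12-month surveys ask about antibiotics given. This stands as a limit on the point. However, the source of the fill data is not stated, the surveys come months later, and neither is linked to the delayed-reaction analysis.

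It is also fair to say that Hypotheses 2a and 2b are contact-rate targets, which adherence does not affect. The study is descriptive, and limits of 30.8% and 41.0% are both wide. That limits the consequence within the prescribed group. It does not answer the contrast with 7.1%, nor the fact that Aim 2 itself asks about repeated doses.

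**Conclusion.** The point holds in this form: the plan does not provide for recording post-discharge exposure at day 7, and it leaves the delayed-reaction denominator undefined. Followed as written, the reported rate can mix children with repeated exposure, children with none after the challenge dose, and children on another antibiotic. It can then understate the rate that Aim 2 seeks.

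The larger effect comes from the denominator: with no events, the upper limit is 7.1% on 50 children against 30.8% on 10. Incomplete courses move it further, to between 33.6% and 41.0%, if 10% to 30% of prescribed children took no repeated doses. That range is an assumption. The figures also take the 10 as penicillin prescriptions, which Section O does not say; any that are not reduce the repeated-penicillin denominator further. The direction of the bias assumes that late reactions are rarer in children without repeated exposure. The contact-rate hypotheses stand unchanged.

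One inconsistency belongs with this point. Section D, Aim 2, step 3 ties the day-7 call to a penicillin prescription, while Section B, the Aim 2 statement in Section D and Section F extend it to any antibiotic.

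**What to change.** 1. Add fixed items to the day-7 call: prescription filled (yes/no), drug, number of days taken, stopped or switched (date and new drug), and the reason, with suspected reaction as a named option. If the existing form already has these items, say so in Section O.
2. In Section O, report delayed reactions with an exact 95% confidence interval among children who took at least one dose of a penicillin after the challenge dose, and show days taken. Report single-dose children and children on another antibiotic separately, and list those who never filled the prescription.
3. List any stop or switch for a suspected reaction beside the reaction count.
4. Reconcile the sections on which prescriptions trigger the day-7 call.

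The cost is a few questions on a call already planned and a few table rows. The downside is a smaller denominator and a wider interval, which shows how little repeated-dose information about 10 children can give. Exposure is best asked at day 7, since recall at 6 or 12 months is a poor substitute.

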★ Nursing and research staff will screen for questionnaire eligible patients

● If nursing questionnaire is not done, research staff to obtain consent for the questionnaire

1) Trained research staff will review the medical records of children in the PED for reported penicillin allergy and other inclusion/exclusion criteria and discuss any patient with the treating attending physician/nurse practitioner/physician assistant. If nursing has administered an allergy questionnaire (on secure CHW computers in the EDTC directly into EPIC), the study team will approach eligible patients (as determined by the nursing questionnaire results in EPIC) to obtain consent/assent for the oral challenge only.

2) If the nursing staff did not implement the questionnaire, research staff will approach for consent/assent including both the questionnaire and the oral challenge per the full protocol. They will also express that their PED physician/nurse practitioner/physician assistant is available to answer any clinical questions the family may have and will facilitate that contact if requested. The Oral Challenge consent will also ask permission to contact families for later follow-up as outlined in Aim 3.

3) Research staff is present in the PED 16 hours per day on weekdays and 10 hours per day on weekends allowing for more than sufficient coverage to meet enrollment goals. We will limit administration of the oral challenge to 3 patients per day in an attempt to limit PED flow disruption. Administration of the questionnaire alone should not be disruptive to flow.

- 4) The questionnaire includes a “yes/no” option about interest in an oral challenge with penicillin if the patient is deemed eligible. Patients who indicate an interest will have their chart and the questionnaire results reviewed by the PED physician/nurse practitioner/physician assistant . If the parent reports the child had symptoms of allergy that place them into a low-risk group for true allergy, they will be eligible to be offered an oral challenge in the PED. If any high-risk symptom of allergy is identified, no oral challenge will be offered (Table 1). For patients with complex past medical histories or symptoms listed as “other”, their chart will be reviewed by the PED physician/nurse practitioner/physician assistant, and their eligibility to be tested will be determined before proceeding at their discretion.

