All adverse events associated with allergy oral challenge will be monitored in the study protocol and reported to the study principal investigators in real time. The patient will be observed immediately after the administration of the oral challenge for signs of allergic reaction such as rash, airway compromise, increased irritability or any other change in status. Prior to discharge from the Pediatric ED patients will again be assessed for any adverse effects of the allergy challenge. True IgE mediated allergic reactions of penicillin are reported to occur less than 0.0014% of the time. However, there is a possibility that an allergic reaction may occur. [name], [name], [name] and [name] will review the data after any reaction requiring ED care. If a patient requires treatment in the PED or inpatient hospitalization following allergy oral challenge this will be reported to the IRB as a serious adverse event. The study investigators will also review the data after every reaction to determine if there is a pattern of questionnaire responses that could predict a reaction. If we determine/suspect any specific low risk patient symptoms are predisposing the population to a systemic reaction, it will be removed from the questionnaire as "low risk" and transferred to the "high risk" symptoms where patients are not deemed testable.

K. ANTICIPATED BENEFITS ASSOCIATED WITH THE PROTOCOL (*value or desired outcome / advantage*) TO HUMAN RESEARCH PARTICIPANTS AND SOCIETY (*medical, psychosocial, altruistic*)

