Benefits to Participants: If patients agree to take part in this study, there is a potential direct medical benefit to the patient in knowing whether or not they are truly allergic to penicillin. From the survey: we will have a better understanding of the symptoms that lead to a report of antibiotic allergy. This won't lead to direct benefit to the child. From the challenge: if they are found not to be allergic it increases the ability to prescribe a class of antibiotics that is often the first line for common pediatric bacterial illnesses. Benefits to Society: We anticipate the information learned from this study will identify a low risk population of patient's who report an allergy to penicillin and are actually not allergic. This would lead to a direct benefit to the medical community by increasing the ability to prescribe penicillin in the setting of common bacterial infection when someone has a reported allergy to penicillin. This not only provides the appropriate treatment of common bacterial infections but also is likely a more cost-effective approach as second- and third-line antibiotics are often more expensive with a wider range of antimicrobial activity leading to the development of resistance.

L. STOPPING POINTS THAT WOULD NOT ALLOW THE STUDY TO CONTINUE AS PROPOSED

The study will be stopped once our sample size has been accrued.

M. IS THERE A DATA SAFETY MONITORING BOARD IN PLACE? WHO ARE IT'S MEMBERS? HOW OFTEN DO THEY MEET?

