[name] will monitor for overall safety throughout the study duration and will review safety data each time 10 subjects are enrolled in the oral challenge group. The patient will be observed immediately after the administration of the oral challenge for signs of allergic reaction such as rash, airway compromise, increased irritability or any other change in status. Prior to discharge from the Pediatric ED patients will again be assessed for any adverse effects of the allergy challenge. [name], [name], [name] and [name] will review the data after any reaction requiring ED care. If a patient requires treatment in the ED or inpatient hospitalization following allergy oral challenge this will be reported to the IRB as a serious adverse event. The study investigators will also review the data after every reaction to determine if there is a pattern of questionnaire responses that could predict a reaction. If we determine/suspect any specific low risk patient symptoms are predisposing the population to a systemic reaction, it will be removed from the questionnaire as “low risk” and transferred to the “high risk” symptoms where patients are not deemed testable.

N. DESCRIBE HOW THE CONSENT AND ASSENT PROCESS WILL TAKE PLACE. INCLUDE A LIST OF APPROPRIATELY TRAINED PERSONNEL WHO WILL BE INVOLVED.

Trained research staff will review the medical records of children in the PED for reported penicillin allergy and other inclusion/exclusion criteria and discuss any patient with the treating attending physician. If nursing has administered an allergy questionnaire (on secure CHW computers in the EDTC directly into EPIC), the study team will approach eligible patients (as determined by the nursing questionnaire results in EPIC) to obtain written informed consent/assent for the oral challenge only.

If the nursing staff did not implement the questionnaire, research staff will approach for written informed consent/assent including both the questionnaire and the oral challenge per the full protocol. They will also express that their PED physician is available to answer any clinical questions the family may have and will facilitate that contact if requested. The Oral Challenge consent will also ask permission to contact families for later follow-up as outlined in Aim 3.

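### Section L names completed accrual as the only stopping point, and nothing in the plan pauses oral challenges while a severe reaction is under review

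*Combined protocol and SAP*

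**What the plan says.** Section L is headed as the place for stopping points, and its full content is "The study will be stopped once our sample size has been accrued". The sample size justification in Section O adds one more ending, also based on reaching the enrolment goal.

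Safety handling is in Sections J and M:

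- Adverse events from the challenge are "reported to the study principal investigators in real time".
- If a child needs treatment in the emergency department or admission, "this will be reported to the IRB as a serious adverse event".
- Named investigators review the data after any reaction that needs emergency care. In addition, "The study investigators will also review the data after every reaction to determine if there is a pattern of questionnaire responses".
- "If we determine/suspect any specific low risk patient symptoms are predisposing the population to a systemic reaction", that symptom moves to the high-risk list and children reporting it are no longer challenged.
- Section M adds that one named person "will review safety data each time 10 subjects are enrolled in the oral challenge group".

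Section D, Aim 1, item 3 states: "We will limit administration of the oral challenge to 3 patients per day in an attempt to limit PED flow disruption". Item 6 requires a trained provider to order each dose, item 7 sets 60 minutes of observation, and item 9 and Section H cover treatment of a reacting child. Section G classes the study as greater than minimal risk in children, with a prospect of direct benefit.

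**The concern.** Reaching the sample size is a planned end. It does not say what would keep the study from going on. The plan accepts that its low-risk list may prove wrong in part, because a reaction can lead to a symptom being reclassified. That correction protects the next child only if it comes before the next dose. No section gives a deadline for the review or says that challenges wait for it.

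At stake is the order of events after a severe reaction: review first and next challenge second, or the reverse. Section H lists anaphylactic shock among the risks, and eligibility rests on parent-reported history. The order is therefore worth fixing in advance, with the same instruction for every shift and any added site.

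**Working it through.** **1. What follows each safety step, as written**

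| Step | Where | Effect on the next child |
|---|---|---|
| Real-time report to the principal investigators | J | None stated |
| Review after a reaction | J, M | None until it ends; no deadline |
| IRB report | J, M | None stated; the IRB could act |
| Symptom moved to high risk | J, M | Ends challenges for that symptom, once determined or suspected |
| Review every 10 challenged children | M | No decision criterion stated |
| Provider's order | D, item 6 | Case by case |
| Accrual complete | L | Study ends |

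No row holds dosing between the event and the end of its review.

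**2. The plan's accrual rate (Section E)**

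50 approached per month × 0.80 = 40 agreeing; 40 − 10 high-risk = 30 low-risk; 30 × 0.50 = 15 challenges per month. 100 / 15 = 6.7 months, which matches the stated 7 or so.

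**3. Children challenged while a review runs**

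Number = monthly rate / 30.4 × review days. The review time is assumed, since the plan gives none.

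| Review time | Planned 15 per month | No refusals, 30 per month |
|---|---|---|
| 1 day | 0.49 | 0.99 |
| 7 days | 3.45 | 6.91 |

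The review every 10 children does not close this gap: at 15 per month it falls about every 10 / 15 × 30.4 = 20 days.

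**4. How often a hold would fire**

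P(at least one trigger) = 1 − (1 − p)^n, with n = 50 (Section O) or n = 100 (one site, Section E). The documents give no severe-reaction rate for this group, so every p is an assumption.

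| Assumed p | Source | n = 50 | n = 100 |
|---|---|---|---|
| below 0.0014% | Section J | below 0.07% | below 0.14% |
| 0.004% | Section D, item 9 | 0.20% | 0.40% |
| 0.015% | Section D, item 9 | 0.75% | 1.49% |
| 0.45% | upper limit from 0/818 | 20.2% | 36.3% |

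Section J puts the first figure this way: "True IgE mediated allergic reactions of penicillin are reported to occur less than 0.0014% of the time". The last row uses the paediatric graded-challenge cohort in Section C, which had 48 reactions in 818 children, none serious. The exact two-sided 95% upper limit for 0/818 is 1 − 0.025^(1/818) = 0.0045.

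**The case against.** The strongest reply is that the plan already protects later children. Mere suspicion is enough to move a symptom to high risk, which ends dosing for that class. A trained provider must order every challenge and may decline; Section E allows for provider refusal and Section O records it. The investigators or the IRB could halt the study at any time. Severe reactions should also be rare in a preselected group: all 100 children in the earlier study with this questionnaire tested negative, and the second cited series (461 patients) had only mild reactions. Naive pooling of the three series gives 0/1,379 and an upper limit of 1 − 0.025^(1/1379) = 0.27%, or 12.5% for n = 50, though the populations differ.

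All of this stands, and it limits the point. It does not remove it, because symptom transfer follows the review, and provider refusal or an ad hoc halt is permitted but not required.

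A reader might infer more than the documents support:

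- *That the study has no safety monitoring, or that nothing can end dosing.* Sections J and M show otherwise.
- *That 21 children could be challenged in a week (3 × 7).* The daily cap is there for department flow and is no accrual forecast. Planned accrual gives about 3.5 a week, and about 7 with no refusals.
- *That a severe reaction is likely.* The 0.45% is a confidence limit from a cohort not described as selected by this questionnaire. It is not an expected rate.

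**Conclusion.** The point holds in a narrow form. Accrual is the only stated stopping point, and no section pauses challenges while a severe reaction is reviewed. Followed as written, the plan allows a child to be dosed before a review that might have excluded that child. The exposure is about 3.5 children per week of review at planned accrual and about 7 with no refusals; the length of the review is assumed.

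The absence of the text is certain. The chance that it would ever matter is not: under 1% in 50 children at the cited incidences, which do not describe challenged children, and up to about 20% at the upper limit from 0/818. The case for a hold depends on none of these rates. No endpoint, sample size or analysis is affected, and the finding does not show the study to be unsafe. It is a gap that should be closed.

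**What to change.** Keep accrual as the planned end and add to Section L:

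> Further oral challenges at the site are held after any anaphylaxis, epinephrine use or hospitalisation for a systemic allergic reaction that occurs by the day 1 follow-up (or by day 7 in children discharged on an antibiotic) and is judged possibly related to the challenge or to a penicillin prescribed after it, until the review in Sections J and M is complete and the event has been reported to that site's IRB; other sites are notified at once.

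Isolated mild reactions, such as a rash alone, do not trigger it. The time windows follow the existing calls, and the relatedness condition keeps out later reactions to unrelated drugs. The site wording suits Section D, which does not expect a single IRB.

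The cost is a short amendment that relies on a review and report already required. Each week of pause delays about 3 to 4 challenges at 15 per month. If triggers proved more frequent than expected, each pause would still follow a possibly related severe event.
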